### 4.3 Justification for Dose

#### 4.3.1 Starting Dose for This Study

In the absence of a reliable pharmacodynamic marker for both ERKi and MEKi, variability in PK alone was also used to guide starting dose.

MK-8353 starting dose will be 50 mg BID with 4 days on/3 days off intermittent dosing schedule. This was selected based on PK simulations of MK-8353 indicated that 50 mg BID would be the highest dose where there is no overlap in the interquartile range of exposure from the 350 mg BID dose could be expected (MTD of MK-8353 monotherapy was 350 mg BID with continuous dosing [PN001]).

The starting dose for selumetinib is planned to be 25 mg BID with 4 days on/3 days off intermittent dosing schedule. PK simulations indicated that the interquartile range of exposures at 25 mg BID would have a separation from exposures at 75 mg BID dose (monotherapy selumetinib MTD = 75 mg BID continuous dosing).

In addition, in the clinical evidence of cobimetinib (MEKi) + GDC-0994 (ERKi) trial, [Weekes, C. D., et al 2017] started at 2/3 cobimetinib and 1/2 of GDC-0994 of the RP2D with 21 days on and 7 days off dosing schedule, and had 1 DLT observed [Weekes, C. D., et al 2017]. Therefore, a more conservative approach is to have a starting dose at 1/5 of the MTD of MK-8353 and 1/3 of the MTD of selumetinib with an intermittent dosing of 4 days on/3 days off.

#### 4.3.2 Maximum Dose/Exposure for This Study

The maximum dose of MK-8353 for this study will be 250 mg administered orally BID, on a 4 days on followed by 3 days off schedule (maximum 500 mg total per day). The Phase 2 dose for MK-8353 monotherapy is 350 mg BID administered continuously. This will provide a total dose of 6000 mg per 3-week cycle which is less than monotherapy dose per 3-week cycle (14700 mg).

The maximum dose of selumetinib for this study will be 125 mg administered orally BID, on a 4 days on followed by 3 days off schedule (maximum 250 mg total per day). The Phase 2 dose for selumetinib monotherapy is 75 mg BID administered continuously. This will provide a total dose of 3000 mg per 3-week cycle which is less than monotherapy dose per 3-week cycle (3150 mg).

Inhibition of both MEK and ERK may exacerbate toxicity of either inhibitor alone. However, intermittent dosing schedules of both MK-8353 and selumetinib (4 days on followed by 3

days off schedule) is likely to be better tolerated than continuous dosing and short half-lives (approximately 8 hours) would reduce concerns over toxicity while maintain anti-tumor activity [Xue, Y., et al 2017].

### 4.3.3 Rationale for Dose Interval and Study Design

MK-8353 will have 50 mg incremental dose levels up to 250 mg (50, 100, 150, 200, 250 mg BID). Selumetinib will have 25 mg incremental dose levels up to 125 mg (25, 50, 75, 100, and 125 mg BID). These follow incremental increases of 100%, 50%, 33% and 25%. The smaller increases at higher doses take into consideration the risk for greater overlapping toxicity.

An alternate dose level, frequency drug administration and dosing schedule may be explored, and an optimal dose will be selected based on totality of data (PK, pharmacodynamic, and safety) emerging throughout the trial. The protocol will be amended as required.

The 4 days on/3 days off schedule was selected based on 1) a preclinical evidence that 4 days on/3 days off with vemurafenib (RAFi), trametinib (MEKi), SCH984 (ERKi) which was shown to ameliorate toxicity and sustain efficacy [Xue, Y., et al 2017]. In this study, continuous MEK/ERK/BRAFi administration was toxic and sequential ERK/MEK inhibition fosters resistance and was less effective, 2) the most common safety signal we see for MAPK pathway is skin rash, usually start seeing early time like from approximately 7 days after the treatment and within 3 month [Wang, D., et al 2007], 3) the short half-life of selumetinib and MK-8353 (approximately 8 hours) suggests that selumetinib and MK-8353 would be eliminated in as long as 2 days after stopping treatment, therefore, have the potential advantage to exploit intermittent schedules that have (preclinically) been shown to ameliorate toxicity but maintain anti-tumor activity [Xue, Y., et al 2017].

### 4.3.4 Dose Finding Using a Modified Toxicity Probability Interval Design

The modified toxicity probability interval (mTPI) design [Ji Y, Li Y, Bekele BN 2007] with a target DLT rate of approximately 30% will be applied to identify the MTD in each of the studied dose combination sequences described above.

In each dose combination sequence separately, dose escalation and de-escalation decisions will be based on the mTPI design and will depend on the number of participants enrolled and number of DLTs observed at the current dose combination level. The number of DLTs will be based on the DLT evaluable population which consists of participants who finished Cycle 1. See Section 5.6 and Section 9.5.1 for details.

A minimum of 3 participants will be required at each dose combination level. However, depending on the accrual rate, 3, 4, 5, or 6 participants may be enrolled at each new dose combination level. In Table 2, the columns indicate the numbers of participants treated at the current dose combination level, and the rows indicate the numbers of participants experiencing DLT. The entries of the table are the dose-finding decisions: E, S, D, and DU represent escalating the dose, staying at the same dose, de-escalating the dose, and excluding the dose from the trial due to unacceptable toxicity, respectively. For example, if 0 out of

3 participants at a given dose combination level develop a DLT, then the dose can escalate to the next level. If 2 participants out of 3 develop a DLT, the dose will be de-escalated to the next lower dose level. If 3 out of 3 participants develop a DLT, this indicates an unacceptable toxicity at this dose combination. The dose combination should be de-escalated, and the current dose combination will not be explored further. If 1 out of 3 participants at a given dose combination level develops a DLT, then additional participants should be enrolled at that dose combination level following the rules below.

When adding participants to a dose combination level in response to a “stay” decision, the number of additional participants to be enrolled is capped to minimize the exposure to a dose combination that may be unacceptably toxic (denoted as DU in [Table 2](#)). Secondly, to determine how many more participants can be enrolled at the dose combination level, one can count steps in diagonal direction (down and to the right) from the current cell to the first cell marked DU. For example, if 1 of 3 participants have experienced a DLT at a given dose combination level, no more than an additional 3 participants should be enrolled at this dose combination level until additional DLT data are available. This is because this dose combination level would be considered unacceptably toxic if all 3 of the additional participants experience a DLT (ie, 4/6 participants with DLT in [Table 2](#)). The same principles will be applied whether 3, 4, 5, or 6 participants are initially enrolled at that dose combination level.

A D or DU decision at the lowest dose combination level will stop the trial. An E decision at the highest dose combination level will result in staying at that level. During dose finding, it may be acceptable to deescalate to an intermediate dose combination that was not predefined and not previously-studied if evaluation of toxicity at such a dose combination is desired. If this approach is taken, 3 to 6 new participants may be enrolled at the new intermediate dose combination, and the rules should be used to determine further enrollment at this dose combination level.

Dose finding will end after 14 participants have been enrolled at any of the tested dose combinations, in each sequence separately, regardless of subsequent dose escalation decision.

The DLT rates across dose combination levels will be estimated under the assumption of a monotonic relationship between toxicity and dose in each column, in each row and along the main diagonal of the dose combination grid. In each dose combination sequence, the dose combination with an estimated DLT rate closest to 30% will be treated as a preliminary MTD. However, the totality of the data will be considered before deciding on the dose(s) to carry forward into the planned expansion phase, and the escalation schedule may be adjusted based on PK, pharmacodynamic, and safety data emerging throughout the trial.

Note that although 30% was the target toxicity rate used to generate the guidelines in [Table 2](#), the observed rates of participants with DLTs at the MTD(s) may be slightly above or below 30%.

Dose escalation decisions will be made upon ongoing review of available PK, pharmacodynamic, and safety data at the current dose level.

Based on the emerging safety and/or efficacy signals, lower, intermediate or higher dose combination levels may also be explored in consultation and agreement with the investigators and Sponsor. The exact additional dose combinations in each sequence during dose escalation is not predetermined, which will allow for flexibility in dose escalation based on emerging safety data in the clinical trial. The protocol will be amended as necessary.

Table 2 Dose-finding Rules per mTPI Design

Number of participants with at least 1 DLT	Number of Participants Evaluable for DLT at Current Dose											
	3	4	5	6	7	8	9	10	11	12	13	14
0	E	E	E	E	E	E	E	E	E	E	E	E
1	S	S	S	E	E	E	E	E	E	E	E	E
2	D	S	S	S	S	S	S	S	E	E	E	E
3	DU	DU	D	S	S	S	S	S	S	S	S	S
4		DU	DU	DU	D	D	S	S	S	S	S	S
5			DU	DU	DU	DU	DU	D	S	S	S	S
6				DU	DU	DU	DU	DU	DU	D	S	S
7					DU	DU	DU	DU	DU	DU	DU	D
8						DU	DU	DU	DU	DU	DU	DU
9							DU	DU	DU	DU	DU	DU
10								DU	DU	DU	DU	DU
11									DU	DU	DU	DU
12										DU	DU	DU
13											DU	DU
14												DU

D = De-escalate to the next lower dose; DU = The current dose is unacceptably toxic; E = Escalate to the next higher dose; S = Stay at the current dose  
 Target toxicity rate = 30%.  
 Flat noninformative prior Beta (1,1) is used as a prior and  $\epsilon_1=\epsilon_2=0.03$  [Ji Y, Li Y, Bekele BN 2007], [Ji, Y. and Wang, S.-J. 2013]

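### Does a D or DU at the start of one off-diagonal sequence stop the whole trial, and what does it do to the diagonal MTD?

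*Combined protocol and SAP*

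**What the plan says.** Section 4.3.4 sets the mTPI rules. It begins with their scope: "In each dose combination sequence separately, dose escalation and de-escalation decisions will be based on the mTPI design". It then defines the four decisions, with DU meaning "excluding the dose from the trial due to unacceptable toxicity", and allows flexible cohorts: "3, 4, 5, or 6 participants may be enrolled at each new dose combination level".

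Three boundary rules follow:
- At the bottom: "A D or DU decision at the lowest dose combination level will stop the trial".
- At the top, an E leads to staying at that level.
- The size limit carries its own scope: "Dose finding will end after 14 participants have been enrolled at any of the tested dose combinations, in each sequence separately".

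The section also gives an optional route downward: "it may be acceptable to deescalate to an intermediate dose combination that was not predefined and not previously-studied".

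DLT rates are estimated assuming monotonicity "in each column, in each row and along the main diagonal of the dose combination grid". Within each sequence, "the dose combination with an estimated DLT rate closest to 30% will be treated as a preliminary MTD". Sections 4.1, 9.1 and 9.6.2 repeat the row-and-column isotonic model. Sections 4.1 and 4.3.4 add that all the data are weighed before any combination goes forward.

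Section 6.3.1 assigns participants alternately to the two off-diagonal sequences after the diagonal has closed, and makes decisions in each sequence independent of the other. Table 1 in Section 4.1 lists the off-diagonal starts, none of which is DL1.

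**The concern.** Two literal readings of the stop rule are possible, and each is awkward.

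- **Lowest means the first level of any sequence.** A D or DU at one off-diagonal start would then end the whole trial. That includes the parallel sequence, which Section 6.3.1 treats as independent.
- **Lowest means DL1 (50/25).** No off-diagonal start is DL1, so the rule would never apply there. Table 2 would send the team to a next lower dose that Table 1 does not list for that sequence.

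The diagonal MTD is also touched. Every start in Table 1 is no higher than that MTD in either drug, and Section 4.2.1 assumes toxicity does not fall as dose rises. A D or DU at a start is therefore evidence about a higher combination already selected. No sentence says whether that selection is then revisited. The diagonal MTD feeds the preliminary RP2D, which is part of the primary objective. The worry is that scope would be settled only after the DLTs are seen.

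**Working it through.** **1. The plan's own figures.** Table 2 was rebuilt from its footnote: Beta(1,1) prior, target 0.30, both epsilons 0.03. DU was taken as posterior P(rate > 0.30) above 0.95; that cutoff is not stated and is an assumption. All 114 filled cells agree. The Section 9.9 totals also follow: 10 × 14 = 140; 3 × (6 + 6 + 14) = 78, given as about 80; 6 × 6 + 14 = 50. No stated figure is in dispute.

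**2. How often the situation arises.** The inputs are Table 2, cohorts of 3 or 6, the Section 4.3.4 cap on additions after a stay (diagonal steps to the first DU), and a maximum of 14 at a level. The true DLT rate at a start is not in the documents, so 10% to 25% is assumed. An exact binomial recursion follows the level until its first E, D or DU, or until 14 participants. For two sequences with equal rates, assumed independent, the chance of at least one is 1 − (1 − q)².

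| True rate at start | q, cohorts of 3 | Either of two | q, cohorts of 6 | Either of two |
|---|---|---|---|---|
| 10% | 3.0% | 5.8% | 0.4% | 0.8% |
| 15% | 6.8% | 13.1% | 1.9% | 3.7% |
| 20% | 12.4% | 23.2% | 5.2% | 10.1% |
| 25% | 19.8% | 35.7% | 11.1% | 20.9% |

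For example, at 20% with cohorts of 3: 1 − (1 − 0.1238)² = 0.232. DU alone, per sequence, at 15/20/25% is 0.6/1.5/3.2% with cohorts of 3 and 0.8/2.4/5.6% with cohorts of 6.

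The two-sequence columns fit a diagonal MTD at DL2, DL3 or DL4. At DL5 one start (200/75) is DL4, already studied. At DL6 only one further sequence opens.

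**3. What the text directs when it arises.** Section 4.3.4 requires de-escalation after 2 of 3 DLTs. After 3 of 3 it requires de-escalation and no further exploration of that combination. These instructions hold under either reading of the stop rule. Only the target below an off-diagonal start is unnamed. The section permits intermediate or lower combinations, and lower diagonal combinations have already been studied.

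**4. Route to the diagonal MTD.** Suppose the diagonal concludes at DL3 (150/75). The start 150/50 shares its selumetinib dose with DL2 (100/50) and its MK-8353 dose with DL3. Row and column ordering alone therefore gives DL2 ≤ start ≤ DL3. Take DL2 at 1/6 = 16.7%.

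- DL3 at 4/14 = 28.6%, start at 2/3 (D). The order is violated, so the two pool: (4 + 2)/(14 + 3) = 35.3%. Distance from 30% is 5.3 points for DL3 and 13.3 for DL2. DL3 stays.
- DL3 at 5/14 = 35.7%, start at 3/3 (DU). Pooled: (5 + 3)/(14 + 3) = 47.1%. Distance is 17.1 points against 13.3, so selection moves to DL2. A 3/3 result has probability 0.20³ = 0.8% or 0.25³ = 1.6% at true rates of 20% or 25%.

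A simulation used 30,000 trials per setting, with assumed diagonal rates 5/15/30/45/55/65/70% and both starts at 20% or 25%. Among trials with the MTD at DL3, re-estimating with the start data changed the selection in 0.9% and 1.9% (cohorts of 3) and 0.9% and 2.6% (cohorts of 6). Among those with a D or DU at a start, it changed in 3.9% to 12.4%.

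**The case for a change.** The best case for a change is that the rule concerns stopping, its trigger is foreseeable, and one sentence would close it. The neighbouring 14-participant rule states its scope and this one does not. Taken literally for each sequence, it conflicts with Section 6.3.1. The phrase limiting MTD selection to each sequence also leaves open whether off-diagonal data re-enter the diagonal estimate. In the first example above, that choice is the difference between 28.6% and 35.3%.

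The drafting criticism stands. Three things limit its weight. The opening scope statement in Section 4.3.4 governs the decision rules that follow. The paired top-level rule points the same way: if it covered only DL7, an E at the top of an off-diagonal sequence would have no consequence. And the frequencies in the table count D or DU decisions, not errors that the wording would cause. The remark about unnamed targets is also narrower than a missing instruction, since de-escalation and exclusion are both prescribed.

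**Conclusion.** The ambiguity is genuine but does not call for a change to the plan. It is a gap that those applying the rules can fill from Sections 4.3.4 and 6.3.1 read together. The stop sentence and the independence statement have to be reconciled when the rule is applied. This note takes no view on which stopping rule is clinically right.

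The diagonal MTD is not left without a method. The row-and-column isotonic model is stated in Sections 4.1, 9.1 and 9.6.2, and the review of all the data stands between any MTD and the RP2D. Whether the diagonal estimate is rerun is the only open part, and it alters the selection in roughly 1% to 3% of simulated trials with the MTD at DL3.

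The conclusion rests on assumed start rates of 10% to 25%, independence of the two sequences, and assumed diagonal rates in the simulation. Figure 1B is not reproduced in the available text and may settle the scope outright. Table 1, Table 2, the estimator and the planned sample size are unaffected.

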## 4 STUDY DESIGN

### 4.1 Overall Design

This is a Phase 1b, multicenter, worldwide, open-label study of MK-8353 in combination with selumetinib in participants with histologically or cytologically confirmed diagnosis of advanced solid tumor. This study will evaluate the safety, tolerability, and preliminary efficacy of MK-8353 in combination with selumetinib.

The dose escalation will start in the sequence of dose combinations formed along the diagonal of the dose combination grid denoted by ① in [Figure 1A](#)): (DL1, MK-8353 50 mg + selumetinib 25 mg), (DL2, MK-8353 100 mg + selumetinib 50 mg), (DL3, MK-8353 150 mg + selumetinib 75 mg), (DL4, MK-8353 200 mg + selumetinib 75 mg), (DL5, MK-8353 200 mg + selumetinib 100 mg), (DL6, MK-8353 250 mg + selumetinib 100 mg), and (DL7, MK-8353 250 mg + selumetinib 125 mg). The mTPI design with a target dose-limiting toxicity (DLT) rate of approximately 30% will be applied to identify a potential MTD in this sequence of dose combinations. If following the mTPI design the dose escalation along the diagonal of the dose combination grid concludes at either the starting dose, (DL1, MK-8353 50 mg + selumetinib 25 mg), or the last dose on the diagonal sequence, (DL7, MK-8353 250 mg + selumetinib 125 mg), the study will end with one MTD only. Otherwise, the study will simultaneously initiate additional off-diagonal dose combination sequences to identify additional potential MTDs as detailed in [Table 1](#) and [Figure 1B](#) ([Table 1](#)). Following [Table 1](#) and [Figure 1B](#), if the dose escalation along the diagonal is concluded at either DL2, DL3, DL4, or DL5, two simultaneous off-diagonal dose combination sequences will be initiated with the respective starting doses specified in [Table 1](#). The complete sequence for each possible scenario is found in [Figure 1B](#). Thus, to identify MTD②, MK-8353 will be escalated while keeping selumetinib fixed. To identify MTD③, selumetinib will be escalated while keeping MK-8353 fixed. If the dose escalation along the diagonal is concluded at DL6, only one additional sequence will be explored using the mTPI decision rules by keeping MK-8353 fixed at 150 and escalating selumetinib: MK-8353 150 mg/100 mg selumetinib and MK-8353 150 mg/125 mg selumetinib.

Table 1 Starting Doses for MK-8353 or Selumetinib Escalation to Potential MTD② and MTD③

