MTD ① per mTPI	Starting dose for MK-8353 escalation to potential MTD ② (see Figure 1B)	Starting dose for Selumetinib escalation to potential MTD ③ (see Figure 1B)
DL1	No additional escalation	No additional escalation
DL2	100 mg MK-8353/25 mg selumetinib	50 mg MK-8353/50 mg selumetinib
DL3	150 mg MK-8353/50 mg selumetinib	100 mg MK-8353/75 mg selumetinib
DL4	150 mg MK-8353/50 mg selumetinib	100 mg MK-8353/75 mg selumetinib
DL5	200 mg MK-8353/75 mg selumetinib	150 mg MK-8353/100 mg selumetinib
DL6	No additional escalation a	150 mg MK-8353/100 mg selumetinib
DL7	No additional escalation	No additional escalation

a ERKi escalation per Figure 1B is not required because highest dose of ERKi is tolerable at DL6.

The rationale for conducting the dose escalation along these sequences is given in Section 4.2.1.

In each of the off-diagonal sequences, the mTPI design with a target DLT rate of approximately 30% will be applied to identify a potential MTD. Based on the emerging safety and/or efficacy signals, other dose levels may also be explored in consultation and agreement with the investigators and Sponsor.

The DLT rates across different dose combinations, in each dose combination sequence, will be estimated using isotonic regression under the assumption of monotonicity between the DLT rates and dose levels in each row and in each column of the dose combination grid [Dykstra, R. L. 1982]. This dose escalation study may yield multiple MTDs. The totality of the data will be considered before deciding on the dose combinations(s) to carry forward to further development (ie, preliminary RP2D).

Upon identification of the preliminary RP2D(s) for the MK-8353 and selumetinib combination, additional participants with solid tumors will be enrolled in the dose expansion

phase of this trial. Participants in the expansion phase of this study will receive MK-8353 in combination with selumetinib as dual therapy.

Preliminary efficacy will be evaluated using objective response rate (ORR) and progression-free survival (PFS) assessed by the investigator based on the RECIST Version 1.1 as exploratory objectives. Overall survival (OS) will also be evaluated as an exploratory objective.

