### **9.6.2 Statistical Methods for Safety Analysis**

Safety and tolerability will be assessed by clinical review of all relevant parameters including AEs, SAEs, laboratory tests, vital signs, ECG measurements, and physical examinations.

Adverse events will be summarized by counts and frequencies for each dose level. Laboratory tests, vital signs, and other safety endpoints will be summarized as appropriate.

Dose limiting toxicities will be listed and summarized by dose level. The DLT rates across different dose combinations, in each dose combination sequence, will be estimated using isotonic regression under the assumption of monotonicity between the DLT rates and dose levels in each row and in each column of the dose combination grid [Dykstra, R. L. 1982]. The estimate of the DLT rate among participants treated at the RP2D and the 80% Bayesian credible interval based on a prior distribution of Beta (1,1) for the estimate will be provided.

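### Does the rule that picks the level closest to a 30% DLT rate need to state whether observed rates or Beta(1,1) posterior means enter the isotonic regression?

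*Combined protocol and SAP*

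**What the plan says.** Section 4.3.4 selects as follows: "In each dose combination sequence, the dose combination with an estimated DLT rate closest to 30% will be treated as a preliminary MTD". Section 4.1 gives the estimator: "The DLT rates across different dose combinations, in each dose combination sequence, will be estimated using isotonic regression", with monotonicity assumed along each row and column of the grid. Section 9.6.2 repeats this.

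The Beta(1,1) prior appears in two places. The footnote to Table 2 (the mTPI decision rules) says "Flat noninformative prior Beta (1,1) is used as a prior". Section 9.6.2 says that for the DLT rate at the RP2D "the 80% Bayesian credible interval based on a prior distribution of Beta (1,1) for the estimate will be provided".

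Section 4.3.4 also notes that "the observed rates of participants with DLTs at the MTD(s) may be slightly above or below 30" percent, defines DU as "excluding the dose from the trial due to unacceptable toxicity", and sets the stop: "Dose finding will end after 14 participants have been enrolled at any of the tested dose combinations", separately in each sequence. It adds that the totality of the data will be considered before doses go forward to expansion.

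On the next step, Section 4.1 says that "if the dose escalation along the diagonal is concluded at either DL2, DL3, DL4, or DL5, two simultaneous off-diagonal dose combination sequences" will be started. The first column of Table 1 is headed by the diagonal MTD per mTPI.

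**The concern.** Isotonic regression needs an input and weights, and the plan names neither. It gives no tie rule either, although pooling adjacent levels produces ties. Observed proportions are one candidate. Posterior means under Beta(1,1) are another, since that prior drives the escalation decisions and underlies the interval reported beside the final estimate.

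Beta(1,1) has mean 50%, so with 3 to 6 participants it pulls a low observed rate up strongly: 0/3 becomes 20%. A sparsely tested low level can then look closer to 30% than a level with 14 participants. The preliminary MTD feeds the primary objective of establishing preliminary RP2D(s). The Table 1 heading could also suggest that the off-diagonal starting doses depend on the named MTD.

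**Working it through.** **The plan's own figures.** Table 2 is reproduced by comparing unit probability mass under Beta(1+x, 1+n-x) over 0-0.27, 0.27-0.33 and 0.33-1, with DU when the posterior probability of a rate above 0.30 exceeds 0.95. That cutoff is an assumption; the plan does not print it. All cells for 0 to 8 DLTs and n = 3 to 14 match. The sample sizes in Section 9.9 also follow: 10 × 14 = 140; 3 × (6 + 6 + 14) = 78, stated as about 80; 6 × 6 + 14 = 50.

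**Two reachable outcomes.** Observed rate = x/n; posterior mean = (x+1)/(n+2). The distance from 30%, in percentage points, is in brackets.

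| DLTs | Input | DL1 | DL2 | DL3 | Named |
|---|---|---|---|---|---|
| 0/3, 1/6, 5/14 | x/n | 0% (30) | 16.7% (13.3) | 35.7% (5.7) | DL3 |
| | (x+1)/(n+2) | 20% (10) | 25% (5) | 37.5% (7.5) | DL2 |
| 0/3, 0/3, 6/14 | x/n | 0% (30) | 0% (30) | 42.9% (12.9) | DL3 |
| | (x+1)/(n+2) | 20% (10) | 20% (10) | 43.75% (13.75) | DL1 or DL2 |

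The fitted values equal the inputs in both cases, so weights play no part. Both obey Table 2 and the enrolment cap: 5/14 via 1/3, 2/6, 3/9 and 4/12; 6/14 via 1/3, 2/6, 4/9 and 4/11. Each step is a stay decision.

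**When two adjacent levels disagree.** Take an upper level with 14 participants and a lower level left on an escalate decision. At 4/14 (28.6%) the inputs never disagree. At 5/14 they disagree only if the lower level is 1/6 or 2/11. At 6/14 they disagree if it is 0/3, 0/4, 1/6 to 1/10, 2/12 or 2/13. Disagreement therefore needs an upper level observed above 30%.

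**How often.** Simulation of single sequences with Table 2, the cap, the stop at 14, DU levels excluded, and one tie rule for both inputs (highest tied level when the tied estimate is below 30%). The true DLT curves are assumptions.

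| Setting | Sequences where the inputs differ |
|---|---|
| Cohorts of 3 or 6, some level near or crossing 30% | about 10-22% |
| Cohorts of 4, 5 or mixed 3-6 | about 2-17% |
| All levels well below 30% | about 0-5% |

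Where they differed, posterior means named the lower level. The size depends on the tie rule: sending ties to the lowest level moves one set of runs to 10.8-55.7%, while differences with no tie under either input are 3.0-14.2%. The two-way grid fit was not simulated.

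**What the text supports.** The quantities smoothed are called DLT rates. Beta(1,1) is attached to the Table 2 decisions and to the interval at the RP2D; no sentence attaches it to the regression. The remark about observed rates at the MTD also fits raw input better. In the first outcome the raw choice has an observed rate 5.7 points from 30%, against 13.3 for the posterior-mean choice; in the second, 12.9 against 30. Fitted to observed rates, the rule minimises this distance whenever no pooling occurs.

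**Does it reach Table 1?** Sections 1.2, 4.1, 4.2.1 and 9.9 all start the off-diagonal sequences from the level at which diagonal escalation concludes. The isotonic fit is not part of that step, so the column heading is a matter of wording.

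**The case for a change.** The best case for a change is reproducibility. The trial is open-label, so an input settled at analysis is settled with the DLT counts in view. The effect has one direction: posterior means favour lower levels, often with 6 or fewer participants. The label bears on the primary objective, and stating the input, weights and tie rule would take two or three sentences with no added participants or procedures.

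Much of this stands. The text is silent and the two outcomes above are correct. Writing the convention down would do no harm.

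It still falls short of a fault. The request is only that the sponsor record whichever convention it intends. It does not show that a stated rule errs, and it offers no better method. Read plainly as observed rates, the rule has no second answer apart from ties. Section 9.6.2 has DLTs listed and summarised by dose level, so a reader can recompute the selection under either input. The percentages rest on assumed curves, a supplied tie rule and a one-dimensional fit, so they cannot be read as the chance that this trial would name a different dose.

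**Conclusion.** No change to the plan follows. The isotonic input, weights and tie rule are not stated, and the input can change the named level by the amounts shown under the stated assumptions. An analyst has a natural default: observed rates weighted by the number evaluable, DU levels excluded as Section 4.3.4 already provides, and a conventional tie rule.

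The consequence is bounded. The result is a preliminary MTD; Sections 4.1 and 4.3.4 call for review of the totality of the data before a dose is carried forward; and the off-diagonal starting doses are set by where escalation concludes. Whether the cited method papers fix the input was not checked, and the conclusion does not depend on it.
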